### 2.0 Objectives\*

*2.1 Describe the purpose, specific aims, or objectives of this research.*

*Response: Determine if medium-dose lithium aspartate therapy in an additional 15 patients is associated with similar improvements in blood-based therapeutic*

targets and MRI-based biomarkers as observed in the previous four patients receiving this dosage.

2.2 State the hypotheses to be tested, if applicable.

*NOTE: A hypothesis is a specific, testable prediction about what you expect to happen in your study that corresponds with your above listed objectives.*

Response: Lithium therapy will engage one or more blood-based therapeutic targets and MRI-based disease-progression biomarkers implicated in PD pathophysiology.

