### 3.0 Scientific Endpoints\*

2.1 Describe the scientific endpoint(s), the main result or occurrence under study.

*NOTE: Scientific endpoints are outcomes defined before the study begins to determine whether the objectives of the study have been met and to draw conclusions from the data. Include primary and secondary endpoints. Some example endpoints are: reduction of symptoms, improvement in quality of life, or survival. Your response should **not** be a date.*

Response:

Primary Outcome Measures:

- Clinical Adverse Events assessed at screening, Baseline (BL), and week 24 as well as during a phone call at week 12.
- Blood safety laboratory assessments at screening and week 24 (CBC, CMP, TSH, calcium, ESR, urate, HgA1C and trough serum lithium performed by Kaleida Laboratory Services).
- MRI-based disease-progression biomarkers at BL and week 24:
  - Posterior substantia nigra (pSN), nucleus basalis of Meynert (nbM) and dorsomedial nucleus of the thalamus (DMN-T) free water (FW) levels.
- Blood-based therapeutic targets at BL and week 24:
  - PBMC Nurr1 mRNA levels by real-time polymerase chain reaction (PCR).

Secondary Outcome Measures at BL and week 24:

- PBMC SOD-1 mRNA levels by PCR, PBMC phosphorylated (p) and total (t) levels of pS9 and t-GSK-3 $\beta$ ; pThr308, pS473 and t-Akt (both t and the ratio of p/t will be used for each data point) and plasma interleukin-6 (IL-6) levels by ELISA.
- Trough, steady-state plasma lithium levels assessed by the UB Chemistry Instrument Center utilizing an inductively coupled plasma mass spectrometer (ICPMS) at BL and week 24.
- Clinical Assessments at BL and week 24:
  - Movement Disorder Society-Unified Parkinson's Disease Rating Scale (MDS-UPDRS), Part III (Motor Examination).
  - Parkinson's Anxiety Scale.
  - Geriatric Depression Scale-15.
  - Fatigue Severity Scale.
  - Insomnia Severity Index.
  - Parkinson's Disease Questionnaire-8.
- Montreal Cognitive Assessment (MoCA) at screening and week 24.

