#### Preliminary Data:

Based on the above background, we conducted an open-label, randomized, pilot trial assessing the effects of three lithium dosages for six months on both blood-based therapeutic targets and MRI-based disease-progression biomarkers among 16 PD patients. This study was funded by the Buffalo Blue Sky Coin program. Because of the limited amount of funding, MRI scans could only be assessed on seven patients. Nevertheless, this pilot study's results showed the lithium aspartate dosage of 45mg/day to robustly engage the therapeutic targets of PBMC Nurr1 and SOD-1 and also to be associated with longitudinal *reductions* in pSN, DMN-T and nbM FW.

In this pilot trial, 16 PD patients were randomized to "low-dose" or "medium-dose" lithium aspartate (15mg or 45mg/day, respectively) or "high-dose" lithium carbonate therapy titrated to a target trough serum lithium level of 0.4-0.5mmol/L for 24-weeks (clinicaltrials.gov: NCT04273932). Three additional PD patients

served as controls and did not receive lithium for 24-weeks. Among the six patients receiving medium-dose lithium, two withdrew due to side effects of sedation and brain fog. No other patients reported side effects. One of the patients who withdrew subsequently resumed lithium aspartate at 30mg/day and reported no side effects with a steady-state trough serum lithium level <0.1mmol/L.

[figure not shown]
Results showed PBMC Nurr1 mRNA levels increased by 420%, 679%, 93% and 139% in the high, medium and low-dose lithium and control groups, respectively, after 24-weeks. Because an *in vitro* study showed that a 180% increase in Nurr1 protected neuronal cells from rotenone-induced death, we defined a “Nurr1 responder” as having a 6-month Nurr1 increase of >200%. With this definition, the Nurr1 responder rates for each lithium dosage and controls were 20%, 75%, 20% and 0%, respectively. Serum lithium levels at six months were 1282, 828, 195 and 0.73µg/L, respectively. In addition, PBMC SOD-1 mRNA increased by 18%, 127%, -1% and 8%, respectively, and by 125% and -21% in Nurr1 responders and non-responders, respectively, after six months. Lithium treatment did not appear to affect PBMC pS9/total glycogen synthase kinase (GSK-3B) ratio levels or plasma alpha-synuclein levels in a dose-response manner.

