## 5.0 Study Design\*

*5.1 Describe and explain the study design (e.g. case-control, cross-sectional, ethnographic, experimental, interventional, longitudinal, observational).*

Response:

We will enroll 15 additional PD patients within five months. Eligible patients will have PD for <4 years diagnosed by a movement disorder specialist (Drs. [name] or [name]), be 45-80 years old, have normal thyroid and renal function at the screening visit, have no previous exposure to lithium therapy, have no history of brain surgery, have no hx of brain imaging findings suggesting another neurological condition besides PD, have no use of tobacco or THC products for >1 year, have stable PD medications for >30 days without current need for adjustments in the investigator's opinion, and have stable psychiatric and diuretic medications for >60 days with no anticipated need for changes for at least 24 weeks.

All patients will receive medium-dose lithium aspartate therapy (30-45mg/day) for 24 weeks ensuring that the study will be completed within 12 months. The following dose titration will be used in order to minimize side effects: 10mg bid x 1 week, then 15mg bid x 1 week, then 20mg bid x 2 weeks, then 20mg qAM and 25mg qhs thereafter. Patients will be contacted weekly over the first 4-6 weeks to assess for side effects that are likely to be due to lithium, such as sedation, dizziness or confusion. If side effects occur and are bothersome to the patient, the dose will be decreased incrementally to a minimum of 30mg/day. Such a design will enable identification of the maximum tolerated dose for study in a future trial and maximize the number of patients receiving the most promising dose (45mg/day) identified in the previous pilot clinical trial. Blood-based biomarkers and MRIs will be assessed at baseline and 24 weeks.

The primary blood-based biomarker outcome measure will be change in PBMC Nurr1 mRNA expression from baseline to 24 weeks, which will be compared with the data from the three control PD patients from the pilot study using ANCOVA. PBMC mRNA expression will be assessed by quantitative real-time PCR using TaqMan probes to match the pilot study's methodology. Based on the

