22% standard deviation among the three control patients and the 540% treatment effect size for the primary outcome from the pilot study results, only two patients would be needed to detect a difference with 95% power at a 2-tailed alpha of 0.05. Secondary outcome measures will include 24-week changes in PBMC SOD-1 expression, PBMC pS9/total glycogen synthase kinase-3B (GSK-3B) and pThr308, pS473 and t-Akt and plasma interleukin-6 (IL-6) levels. Blood-based biomarkers will be assessed by [name]. Statistical analyses will be performed by [name].

The primary MRI outcomes will be 24-week MRI changes in DMN-T, nbM and pSN FW. Using ANCOVA, these outcomes will be compared with the known natural history of such changes in PD derived from the UF and PPMI longitudinal cohorts summarized in Table 1. In addition, secondary comparisons will be made between changes in these lithium-treated patients and age-matched and disease-duration-matched PD subsets from PPMI.

Exploratory clinical outcomes will include changes in Movement Disorder Society-Unified Parkinson's Disease Rating Scale (MDS-UPDRS) Part III (Motor Examination) with subjects in the "on" state, Montreal Cognitive Assessment (MoCA), Parkinson's Anxiety Scale, Geriatric Depression Scale-15, Fatigue Severity Scale, Insomnia Severity Index and Parkinson's Disease Questionnaire-8. Adverse events and medication compliance will be assessed at a three month phone call. Trough serum lithium and safety labs including HgA1C will be assessed at each visit. Because both baseline and on-treatment lithium levels will mostly be below the level of detection using conventional clinical laboratory services (i.e. Kaleida or Quest), these assays will be performed by the UB Chemistry Instrument Center under the direction of [name]. A protocol was developed by Drs. [name] and [name] for these assays for the pilot study that provided reliable results able to detect baseline lithium levels in all patients prior to initiation of lithium therapy.

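### The secondary blood targets have no comparator and no runnable test, so a 24-week change in SOD-1, GSK-3beta, Akt or IL-6 cannot be attributed to lithium

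*Combined protocol and SAP*

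**What the plan says.** All references are to the combined protocol and SAP.

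- **Section 5.1, treatment.** "All patients will receive medium-dose lithium aspartate therapy", so the 15 new patients form one non-randomised arm.
- **Section 5.1, Nurr1.** The primary blood outcome is the 24-week change, "which will be compared with the data from the three control PD patients from the pilot study using ANCOVA".
- **Section 5.1, MRI.** For free water, "these outcomes will be compared with the known natural history of such changes in PD", taken from the UF and PPMI cohorts.
- **Section 5.1, secondary blood targets.** "Secondary outcome measures will include 24-week changes in PBMC SOD-1 expression", followed by GSK-3beta, Akt and IL-6. No comparator, test or threshold is attached to any of them.
- **Section 3.0.** For the phosphorylated markers, "both t and the ratio of p/t will be used for each data point".
- **Section 2.2.** "Lithium therapy will engage one or more blood-based therapeutic targets and MRI-based disease-progression biomarkers implicated in PD pathophysiology". The plan does not define what counts as engaging a target.
- **Section 19.1.** Every outcome is modelled on randomised group assignment. Permutation p-values are used, with Bonferroni-adjusted pairwise comparisons among three treatment groups. There is no adjustment across outcomes.
- **Section 4.1, Preliminary Data.** "PBMC Nurr1 mRNA levels increased by 420%, 679%, 93% and 139% in the high, medium and low-dose lithium and control groups", and, in the same group order, "PBMC SOD-1 mRNA increased by 18%, 127%, -1% and 8%, respectively". No control-group change is shown for GSK-3beta, Akt or IL-6.

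**The concern.** Two of the three families of biomarkers have an outside reference in Section 5.1. The third, the secondary blood targets, has none. Section 19.1 looks as if it should supply one, but its model describes a randomised three-group comparison, and this stage has one group and no randomisation. Read against the pilot, the three groups are the lithium doses. The three untreated controls were additional to the 16 randomised patients, so even the pilot version of that model did not contain them.

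The only result these patients can yield for the secondary targets is a mean change from baseline with nothing to set it against. Such a change mixes any lithium effect with assay drift, regression to the mean, disease course and changes in other treatment.

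Section 2.2 asks for one or more blood targets to be engaged, and Section 3.0 opens seven secondary readouts. The results are meant to support a grant application for a larger randomised trial, so a drift reported as engagement could carry forward into that application.

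**Working it through.** **1. The plan's own figure.** Section 5.1 gives an SD of 22% among the three controls, an effect of 540%, 95% power and two-sided alpha 0.05, and concludes that two patients suffice.

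- n per group = 2 × [22 × (1.960 + 1.645) / 540]² = 0.043, rounded up to 1 per group, or 2 in total. The figure reproduces.
- 540 = 679 − 139. For Nurr1, the effect used is already net of the rise in untreated controls. No sample-size figure is given for the secondary targets.

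**2. Count of secondary readouts (Sections 3.0 and 5.1).** SOD-1; total GSK-3beta and its p/t ratio; total Akt and two p/t ratios; IL-6. That makes 1 + 2 + 3 + 1 = 7.

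**3. How large drift was where it can be seen.** Nurr1 in untreated controls: mean +139%, n = 3, SD 22, read as percentage points of change.

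- Standard error = 22/√3 = 12.70.
- t = 139/12.70 = 10.9 on 2 df, two-sided p = 0.008, 95% CI 84% to 194%.
- The result stays below 0.05 for any SD under 139√3/4.303 ≈ 56 points.

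So a before-after reading of Nurr1 would have been significant with no lithium given. Nurr1 does have a comparator in this plan. The figure shows what an uncontrolled reading can do in this setting; it does not measure the error in the secondary markers.

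**4. What drift would do to an uncontrolled marker in 15 patients.** One-sample t-test, no drug effect, noncentrality = (drift/SD) × √15, 14 df, two-sided 0.05:

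| Drift in SD units | Probability of a significant change |
|---|---|
| 0.25 | 0.15 |
| 0.5 | 0.44 |
| 0.75 | 0.77 |
| 1.0 | 0.95 |

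**5. The one secondary marker with a reported control change.** SOD-1 rose 8% in controls. The documents give no SD, so a range is assumed:

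| Assumed SD (points) | Probability of a significant change from an 8-point drift alone |
|---|---|
| 8 | 0.95 |
| 10 | 0.82 |
| 22 | 0.26 |
| 50 | 0.09 |
| 100 | 0.06 |

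At the larger SDs the risk is close to the nominal 0.05. For GSK-3beta, Akt and IL-6 no such calculation is possible.

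**6. What a comparison with the three pilot controls can detect.** Two-sample t-test, 15 v 3, 16 df, standard error = SD × √(1/15 + 1/3) = 0.632 SD.

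- Minimum detectable difference at 80% power: about 1.89 SD. This ignores any gain from the baseline covariate in an ANCOVA.
- For SOD-1 the pilot difference is 127 − 8 = 119 points. Power is above 0.99 at an assumed SD of 22, 0.94 at 50 and 0.42 at 100.

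**The case against.** The strongest reply has four parts.

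- **No before-after rule is adopted.** A reader might infer that the plan judges these markers by a before-after test. The documents do not say so. They list 24-week changes as outcomes, as they also do for Nurr1 before naming its comparator. The one general inference plan, in Section 19.1, is between-group. This stands. The defect is that no runnable analysis is specified, not that a wrong test was chosen.
- **Drift alone need not satisfy the hypothesis.** A reader might infer that one drifting blood marker meets Section 2.2. The sentence joins blood targets and MRI biomarkers, and the MRI outcomes have an external comparator. On a conjunctive reading, only the blood half could be met by drift.
- **The evidence of drift is borrowed.** The p = 0.008 figure belongs to Nurr1, rests on three patients and depends on the unit read into the 22% SD. A reader might also infer that the untreated controls would have been called engaged. None of them passed the pilot's responder cut of more than 200%. For SOD-1 the control change was small beside that on medium dose. All of this stands.
- **There is a benchmark.** Section 2.1 asks whether the new patients resemble the four earlier patients on this dose, which for SOD-1 means about +127%. A small drift would not resemble that. But the benchmark is itself a treated group, so a change common to both would look like replication, and the plan sets no margin for similarity.

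These are also secondary outcomes in a declared proof-of-concept study. That lowers the stakes, but none of these points supplies the missing comparator.

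**Conclusion.** The point holds in a limited form. For SOD-1, GSK-3beta, Akt and IL-6 the plan contains no analysis that separates lithium from drift: Section 5.1 names no comparator, and the model in Section 19.1 cannot be fitted to a single treated arm.

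The size of the resulting error is unknown for six of the seven readouts. For SOD-1 it runs from negligible to severe, depending on an SD that the documents do not give. The Nurr1 rise in untreated controls shows that large non-drug change can occur in these assays, by analogy only.

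The documents do not support saying that the hypothesis can be met with no drug effect, or that a before-after success rule is in force. What is affected is the blood half of Section 2.2, where engagement is undefined.

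Assumptions: the 22% SD is in percentage points of Nurr1 change; the SOD-1 SDs are an assumed range; changes are treated as roughly normal. The change is worth making because the pilot already reports a control result for SOD-1, and the plan already uses those controls for Nurr1.

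**What to change.** - **Section 5.1.** Compare the 24-week SOD-1 change with the same three untreated pilot controls, by the same ANCOVA as for Nurr1. Do likewise for GSK-3beta where control values exist. Section 5.1 already matches the mRNA assay to the pilot's method, which supports the SOD-1 comparison.
- **Markers without control values.** Report them as descriptive and not as evidence of engagement. This applies to Akt and IL-6 unless stored control samples prove available. Sections 20 and 32 provide for indefinite storage, but the documents do not say that baseline and Week 24 material from the three controls remains.
- **Section 2.2.** State that engagement means a change exceeding that in controls, and say whether the blood and MRI parts must both be met.
- **Section 19.1.** Replace the randomised three-group text with the comparator, model and role (inferential or descriptive) of each outcome.

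The cost is mainly wording, plus assay work if control samples are found. With 15 against 3, only differences of about 1.9 SD are detectable with 80% power, and fewer markers can be claimed as engaged. The controls are few, earlier in time and not randomised, so the comparison reduces the bias but does not remove it.

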**Table 1: Mean FW Longitudinal Changes from Pilot Lithium/PD Trial, UF and PPMI Longitudinal Cohorts**

	Mean Change in DMN-T FW	Mean Change in nbM FW	Mean Change in pSN FW
High-Dose Lithium (24-Week Changes)	-0.0117 (n=2)	-0.0140 (n=2)	0.0198 (n=2)
Medium-Dose Lithium (24-Week Changes)	-0.0098 (n=2)	-0.0416 (n=2)	-0.0307 (n=2)
Low-Dose Lithium (24-Week Changes)	0.0123 (n=2)	-0.0306 (n=2)	0.0787 (n=2)
PD from UF (1-Year Changes)	---	---	0.038  (n=25)
Aged-Matched HCs from UF (1-Year Changes)	---	---	0.001  (n=19)

PD from PPMI (1-Year Changes)	0.0100 ± 0.030  (n=130)	0.0025 ± 0.041  (n=130)	0.0180 ± 0.055  (n=103)
Aged-Matched HCs from PPMI (1-Year Changes)	0.0005 ± 0.024  (n=58)	-0.0085 ± 0.034  (n=58)	0.0070 ± 0.030  (n=49)

FW: free water, PD: Parkinson's disease, UF: University of Florida, PPMI: Parkinson's Progression Markers Initiative, DMN-T: dorsomedial nucleus of the thalamus, nbM: nucleus basalis of Meynert, pSN: posterior substantia nigra, HC: healthy control.

In summary, this pilot study showed medium-dose lithium therapy to have the most robust therapeutic target engagement of PBMC Nurr1 and SOD-1 mRNA expression and the most robust improvements in known MRI disease-progression biomarkers but to also have a high rate of side effects. Also, these results stem from only four and two patients receiving this lithium dosage with blood-based and MRI biomarker data, respectively. If similar results were found in a larger number of PD patients treated with medium-dose lithium therapy in a manner to improve clinical tolerability, such preliminary data would form a strong grant application to the Michael J Fox Foundation and/or the NIH to support a larger RCT.

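### The primary MRI comparison sets 24-week free-water changes against 1-year cohort changes with no common time scale, which biases the estimate towards slowed progression

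*Combined protocol and SAP*

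**What the plan says.** Section 5.1 defines the outcomes: "The primary MRI outcomes will be 24-week MRI changes in DMN-T, nbM and pSN FW". The comparison follows directly: "Using ANCOVA, these outcomes will be compared with the known natural history of such changes in PD derived from the UF and PPMI longitudinal cohorts", with a pointer to Table 1 as the summary of that natural history.

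Table 1 (section 4.1) labels each lithium row "24-Week Changes" and each UF and PPMI row "1-Year Changes".

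A secondary comparison uses PPMI patients matched on age and disease duration. Follow-up interval is not among the matching factors. Section 19.1 does not mention the external cohorts. It describes an ANOVA across randomised groups, so it supplies no time adjustment either. The study has one arm: "We will enroll 15 additional PD patients within five months", all on lithium.

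**The concern.** FW is used because it tends to rise over time in Parkinson's disease. A change measured over less than half the cohort's interval should therefore be smaller even if the drug does nothing. Read as planned, that shortfall counts as benefit, and it runs in lithium's favour in all three regions.

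Slowed FW progression is a conclusion the protocol wants to draw. Section 4.1 says that slowing of the FW increase would mark a promising disease-modifying candidate, and that similar results in more patients would support a grant application for a larger randomised trial. No concurrent untreated arm is being scanned, so nothing inside the study would expose the artefact.

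**Working it through.** The plan states no power, expected difference or sample size for the MRI comparison, so there is no MRI figure of its own to reproduce.

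**Inputs (Table 1, untreated PD, 1-year change; ± read as an SD)**
- PPMI pSN: 0.0180 ± 0.055, n = 103
- PPMI DMN-T: 0.0100 ± 0.030, n = 130
- PPMI nbM: 0.0025 ± 0.041, n = 130
- UF pSN: 0.038, n = 25, no SD given
- Trial: 24 weeks, n = 15 (section 5.1)

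**Step 1. Share of the 1-year rise expected at 24 weeks.** Under linear accrual, 24/52 = 0.4615. Apparent slowing with an inert drug = 1 − 0.4615 = 53.8%.

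**Step 2. Size of the shift.** Expected 24-week change = 1-year change × 24/52; shift = 1-year change − expected change.

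| Region, cohort | 1-year | Expected at 24 weeks | Shift favouring lithium |
|---|---|---|---|
| pSN, PPMI | 0.0180 | 0.0083 | 0.0097 |
| pSN, UF | 0.038 | 0.0175 | 0.0205 |
| DMN-T, PPMI | 0.0100 | 0.0046 | 0.0054 |
| nbM, PPMI | 0.0025 | 0.0012 | 0.0013 |

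**Step 3. Sensitivity of the 54%.**
- Progression shape, with share accrued = (24/52)^k: k = 0.5 gives 32%, k = 0.75 gives 44%, k = 1 gives 54%, k = 1.5 gives 69%.
- Scan windows (section 12.1): the Week 24 scan falls within 10 days of that visit. Assume the baseline scan falls between 21 days before Visit 2 and Visit 2 itself. The interval then runs from 168 − 10 = 158 days to 168 + 10 + 21 = 199 days. Apparent slowing is 1 − 158/365.25 = 57% down to 1 − 199/365.25 = 46%.

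**Step 4. Effect on a test against PPMI.** With equal SDs, SE = SD × √(1/15 + 1/n), and the chance of a significant result favouring lithium is approximately 1 − Φ(1.96 − shift/SE).
- pSN: SE = 0.0152, shift/SE = 0.64, chance 9.3%
- DMN-T: SE = 0.0082, shift/SE = 0.66, chance 9.7%
- nbM: SE = 0.0112, shift/SE = 0.12, chance 3.3%

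Simulated two-sample t-tests of an inert drug (two-sided 0.05, so nominally 2.5% in this direction) give the following. The first figure takes the 24-week SD equal to the 1-year SD; the second reduces it by √(24/52).

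| Region | Unequal-variance test | Pooled-variance test |
|---|---|---|
| pSN | about 9% / 13% | about 9% / 4% |
| DMN-T | about 9% / 14% | about 10% / 4% |
| nbM | about 3% / 4% | about 3% / below 1% |

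**Step 5. UF.** Table 1 gives no UF SD, so a test rate needs an assumed one. By the unequal-variance test, an SD of 0.080 gives about 11-15%, 0.055 (borrowed from PPMI) about 20-27%, and 0.030 from 52% to just over 70%. No single figure can be defended.

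**Step 6. Choice of cohort for pSN.** The two untreated 1-year changes differ by 0.038/0.018 = 2.1-fold. If the trial's patients progress at the PPMI rate but are compared with unscaled UF, apparent slowing is 1 − 0.0083/0.038 = 78%. If they progress at the UF rate but are compared with unscaled PPMI, it is 1 − 0.0175/0.018 = 3%.

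**The case against.** This is a 15-patient, open-label, proof-of-concept study, and the plan is silent on scaling; it does not rule it out. A statistician handling patient-level cohort data might well adjust for the interval as a matter of course. The Table 1 rows are correctly labelled by interval, so nothing is hidden. Against PPMI, with equal SDs, the shift is about 0.65 standard errors for pSN and DMN-T and 0.12 for nbM. With a pooled-variance test and a smaller 24-week SD, the false-positive rate rises only to about 4% for pSN and DMN-T and falls below 1% for nbM. All of this stands, and it limits the size of the concern. It does not remove the shift in the estimate, and the plan nowhere commits to the adjustment.

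Three stronger readings are tempting, and the documents do not support them:
- A reader might take 54% as the chance of a false-positive result. It is the expected distortion of the point estimate, and only under linear accrual.
- A reader might infer that the mismatch explains the pilot's mean FW reductions on the medium dose. It cannot do so by itself: the expected change with an inert drug stays positive (for example 0.0083 for pSN).
- A reader might infer from the missing UF SD that an ANCOVA against UF is impossible. ANCOVA uses patient-level data. Table 1 is only a summary, and section 4.1 says that some cohort data were supplied to the team. What Table 1 does show is that UF offers a pSN value only.

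**Conclusion.** The concern holds. As written, a primary MRI comparison sets a 24-week change against a 1-year change, and the error runs towards a finding of slowed progression. If FW rises linearly and the enrolled patients would progress like the cohort, the apparent slowing with an inert drug is about half. Its effect on significance is moderate for pSN and DMN-T, depends on the test and the 24-week SD, and is practically nil for nbM. The test rates assume 15 analysable patients and that ± denotes an SD. Against UF no single rate can be given. The point bears on claims of slowing; an observed mean decrease in FW would need another explanation. Which cohort should be the primary comparator is a separate design choice that this point does not settle.

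**What to change.** State in sections 5.1 and 19.1 that trial and cohort changes are analysed on one time scale, using actual scan dates. Actual dates also cover the scan windows and any early scans, since section 22.2 asks withdrawn subjects to complete the Week 24 procedures at a final visit.

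- **Preferred:** fit patient-level cohort and trial data together, with time in years, a group-by-time term and adjustment for baseline FW; or use cohort scans taken at a matching interval.
- **If only summary data are available:** multiply the annual change by (days between scans)/365 and carry the cohort's sampling error into the comparison, so that the scaled mean is not treated as a known constant. At 24 weeks the references are pSN 0.0083, DMN-T 0.0046 and nbM 0.0012 for PPMI, and pSN 0.0175 for UF.
- **In either case:** add a sensitivity analysis for non-linear progression, and report pSN against PPMI and UF separately because their 1-year changes differ two-fold.

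The cost is a few sentences and some analysis time, with no new patients, scans or visits. The downside is a stated assumption about the shape of progression and a contrast that will look less favourable to lithium.

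### The primary MRI comparison sets 24-week changes against 1-year cohort changes, ranks the matched PPMI comparison second, and has no rule for choosing between two pSN references that differ 2.1-fold

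*Combined protocol and SAP*

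**What the plan says.** Section 5.1 (Study Design) states: "The primary MRI outcomes will be 24-week MRI changes in DMN-T, nbM and pSN FW". By ANCOVA these are to be "compared with the known natural history of such changes in PD derived from the UF and PPMI longitudinal cohorts summarized in Table 1". The next sentence adds that "secondary comparisons will be made between changes in these lithium-treated patients and age-matched and disease-duration-matched PD subsets from PPMI". No covariates are named for the ANCOVA, and no rule covers pooling UF with PPMI or disagreement between them.

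Table 1 (section 4.1) labels every UF and PPMI entry as a 1-year change and the pilot entries as 24-week changes. For PD patients it gives:

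- pSN: UF 0.038 (n=25, no SD); PPMI 0.0180 ± 0.055 (n=103)
- DMN-T: PPMI 0.0100 ± 0.030 (n=130); no UF value
- nbM: PPMI 0.0025 ± 0.041 (n=130); no UF value

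Section 19.1 does not fill the gap. It describes permutation tests among three randomized groups and mentions no external reference, whereas the new cohort is a single arm of 15.

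**The concern.** The MRI comparison has no concurrent control, so the reference carries the inference. Three choices that affect the answer are open or doubtful.

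1. **Time base.** A 24-week change is to be compared with figures tabulated over 1 year. In a region where FW rises over time, untreated patients would look better than the reference simply because less time has passed.
2. **Which pSN reference.** UF progresses at 2.1 times the PPMI rate, and no rule says which counts. If the choice is made after the data are seen, the pSN result can be significant or not, and a small difference can change sign, on the same treated patients.
3. **Ranking.** Eligibility is restricted ("Eligible patients will have PD for <4 years diagnosed by a movement disorder specialist", Hoehn & Yahr stage 1 or 2, age 45-80 in section 8.1). The one comparison that takes account of age and disease duration is already planned, but it is placed second.

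At stake is whether a primary result offered in support of a larger trial reflects the drug or the choice of comparator.

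**Working it through.** The plan gives no power or precision figure for the MRI outcomes (section 19.2 answers N/A), so there is none to reproduce.

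**Inputs.** Table 1: UF 0.038, n=25; PPMI 0.018, n=103; PPMI ± 0.055, read as an SD; pilot medium-dose pSN mean -0.0307, n=2. Section 5.1: n=15. Section 19.1: two-sided tests at 0.05. Assumptions: one common SD of 0.055, with 0.030 as a sensitivity value, because the UF and treated-group SDs are not given; linear progression when scaling by 24/52; a simple two-sample t comparison in place of the unspecified ANCOVA.

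**Step 1: size of the disagreement.** 0.038/0.018 = 2.11; 0.038 - 0.018 = 0.020 per year. At 24 weeks: UF 0.038 × 24/52 = 0.0175; PPMI 0.018 × 24/52 = 0.0083; gap 0.0092.

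**Step 2: observed mean needed for significant benefit.** SE = SD × √(1/15 + 1/n_ref); threshold = reference mean - t(0.975) × SE, with t = 2.024 on 38 df (UF) and 1.981 on 116 df (PPMI).

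| SD | Time base | SE, UF | SE, PPMI | Threshold, UF | Threshold, PPMI |
|---|---|---|---|---|---|
| 0.055 | 24 weeks | 0.0180 | 0.0152 | -0.0188 | -0.0218 |
| 0.030 | 24 weeks | 0.0098 | 0.0083 | -0.0023 | -0.0081 |
| 0.055 | 1 year as tabulated | 0.0180 | 0.0152 | +0.0016 | -0.0121 |
| 0.030 | 1 year as tabulated | 0.0098 | 0.0083 | +0.0182 | +0.0016 |

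Between the two thresholds in a row, UF gives p<0.05 and PPMI does not. At SD 0.055 the window is about 0.003 wide on the 24-week base and about 0.014 wide if 1-year values are left unscaled.

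**Step 3: false-positive risk.** Suppose an inert drug leaves patients on the PPMI rate, with SD 0.055. The chance of significant benefit, nominally 2.5%, is:

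- both sides at 24 weeks: about 7% against UF, 2.5% against PPMI
- a 24-week change against 1-year values: about 36% against UF, about 9% against PPMI

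The time-base mismatch therefore inflates the error even against PPMI alone.

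**Step 4: limits of the effect.** On the 24-week base at SD 0.055:

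- Observed mean +0.013: 0.0045 below UF (t = 0.25, p about 0.80) and 0.0047 above PPMI (t = 0.31, p about 0.76). The sign differs, but both results are null.
- Observed mean -0.0307 (pilot): p = 0.011 against UF and 0.012 against PPMI. Both are significant.
- Significant harm against PPMI needs a mean above 0.0083 + 1.981 × 0.0152 = 0.0384, far above the UF benefit threshold of -0.0188. No result is significant benefit against one cohort and significant harm against the other.

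**Step 5: precision cost of matching.** Ratio of √(1/15 + 1/m) to √(1/15 + 1/103), for an assumed matched PPMI subset of size m: m=60, +4%; m=45, +8%; m=30, +14%; m=15, +32% (SE 0.0152 to 0.0201 at SD 0.055).

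**The case against.** The strongest case against is that this is a proof-of-concept study, both comparisons are already written down, and section 19.1 disclaims a single primary outcome, so which comparison ranks first is largely preference. Much of the supporting detail stands:

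- The cohort conflict touches one of three primary regions; DMN-T and nbM have a single reference.
- The twofold gap is between UF and the whole PPMI cohort, not between matched and unmatched patients. The documents give no matched-subset mean and no age or duration for either cohort. At SD 0.055 for both, the gap is within sampling error (SE 0.0123, p about 0.10); at SD 0.030 it is not (p about 0.003).
- Section 5.1 says the trial's pSN regions follow the publication that Table 1 cites for UF, so UF is the reference tied to the trial's own method. That argues against discarding it.
- The trial uses a new Philips 3T scanner and a newly optimized diffusion sequence. Matching on age and duration does not remove scanner or pipeline differences.

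A reader might infer that the planned ANCOVA cannot be run because Table 1 has no baseline FW and no UF SD. The documents do not support that for PPMI: Table 1 is described as a summary, and the planned matched subsets imply patient-level PPMI data. For UF, access to individual data is not stated.

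The objection does not answer the absence of a deciding rule for pSN or of a time base for any region. Those gaps change error rates whatever the study's phase.

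**Conclusion.** The concern holds in a limited form. The primary MRI comparison is not specified well enough to give one answer for pSN, it sets 24-week changes against references tabulated over 1 year in all three regions, and it puts the age- and duration-matched comparison second. On a common 24-week base the pSN reference decides significance only in a narrow range: -0.0218 to -0.0188 at SD 0.055, or -0.0081 to -0.0023 at SD 0.030. If the time bases are left unmatched, an inert drug on the PPMI rate would appear beneficial about 36% of the time against UF and 9% against PPMI.

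Two stronger readings are tempting and not supported. One is that the choice of cohort reverses the conclusion: it can change significance, or the sign of a small non-significant difference, but not turn significant benefit into significant harm, and at the pilot mean both references agree. The other is that matching would change the result: the documents give nothing from which to judge that.

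The figures rest on n=15 with no exclusions, a common SD of 0.030 to 0.055, linear progression, and an unadjusted two-sample comparison.

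**What to change.** In section 5.1, and carried into section 19.1:

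1. Make the patient-level PPMI comparison primary for all three regions, either matched on age and disease duration or using all PPMI PD patients with these as covariates. Choose one in advance.
2. Put the reference change on a 24-week time base. If 1-year values are pro-rated, state the linearity assumption.
3. Report UF for pSN as a named sensitivity comparison, noting that the trial's pSN region method follows the UF source. State that it does not decide the primary result.
4. Use baseline FW as a covariate only with a stated caution: offsets between the new scanner and sequence and those of PPMI could bias the adjustment, and matching does not remove them.

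The cost is plan wording, since the matched comparison is already intended, plus some precision: the SE rises about 4% to 14% if 60 to 30 PPMI patients are matched, and 32% if only 15 are (common SD assumed). Covariate adjustment using all PPMI PD patients avoids most of that loss, because the 15 treated patients dominate the SE (0.055/√15 = 0.0142 of a total 0.0152 for pSN).
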